Evidence of Benefit to Society: The importance of the knowledge gained from this protocol is high, since DKD is very prevalent in T1D and increases the risk of death from CVD and shortens lifespan. In fact, T2D in youth is increasing in prevalence in parallel with the obesity epidemic. In the United States, almost half of patients with renal failure have DKD. Despite the high prevalence and gravity of DKD in youth onset T1D, widely effective therapeutic options are lacking. Diabetes mellitus is the third most prevalent severe chronic disease of childhood. DKD remains a leading cause of morbidity and mortality, and a major risk factor for CVD in diabetes. Although data to guide care of DKD in adults with diabetes are limited, even less data exist regarding the antecedents of DKD in youth with diabetes. Yet, these antecedents of adult DKD are present in childhood, data to inform clinicians as to treatment in this high-risk population are of great public health importance. In our novel and innovative proposal, we postulate that coffee will decrease renal oxygen consumption, thereby improving renal oxygenation without impairing GFR and ERPF. Knowledge gained from this proposal will provide new information about the effects of coffee on renal energetics and intrarenal hemodynamic function in T1D. The investigative team is also unique in being one the few groups skilled in performing both gold standard renal physiology studies and advanced MRI evaluation in youth with T1D.

G. Data Analysis Plan (formulated with biostatistician [name] PhD):

Aim 1-2 Power calculations, statistical analysis, rigor and reproducibility: For this initial pilot and feasibility trial, we plan to recruit 10 youth. Power calculations are based on paired *t*-tests. A sample size of 10 provides 80% power to detect a mean paired difference of 0.44 SD for renal oxygenation and tubular injury markers. The following variables will be considered for inclusion in models as confounders: response: age, sex, ethnicity, T2D duration, HbA1c, BP, LDL-C and FeNa. We will use paired *t*-test and McNemar's test in addition to multivariable linear models of the change in each outcome, adjusted for potential confounders. This is a pilot and feasibility study and the data should be considered hypothesis generating. We acknowledge that we may be underpowered for multivariable modeling, and our primary analyses will be unadjusted.

Renal Volume: Using 3D Slicer (SPL, Harvard Medical School, MA), the semi-automated segmentation of kidneys will be conducted initially with a thresholding procedure. Manual editing will then be performed to refine the segmentation of bilateral kidneys by placing straight lines at the convex level to separate the right kidney from liver and to remove bilateral ureters from the kidneys. This editing process will need to be performed on few contiguous slices with limited human interaction. The kidney volume will then be computed as the number of voxels within one kidney multiplied by the voxel size.

BOLD MRI: Regions of interest (ROI) analysis for BOLD MRI will be performed on a Leonardo Workstation (Siemens Medical Systems, Germany). Typically, 1 to 3 regions in each, cortex and medulla, per kidney per slice will be defined leading to a total of about 10 ROIs per region (cortex and medulla) per subject. The mean and standard deviation of these 10 measurements will be used a R_2^* measurement for the region, for the subject and for that time point. Additionally, two ΔR_2^* s will be calculated as defined below:

 ΔR_2^* (medulla, furosemide) = R_2^* (medulla, pre-furosemide) - R_2^* (medulla, post-furosemide);

 ΔR_2^* (cortex, medulla) = Baseline R_2^* (medulla) – Baseline R_2^* (cortex).

ASL MRI: ROI analysis will be used to estimate ΔM (difference in signal intensity between non-selective and selective inversion images). Using the same ROI, M₀ will be estimated from the proton density image. T₁ measurements from the same ROI will be obtained by fitting the signal intensity *vs.* inversion time data as described previously (104) using XLFit (ID Business Solutions Ltd., UK) or T₁ maps created using MRI Mapper (Beth Israel Deaconess Medical Center, Boston). Partition coefficient will be assumed to be 0.8 ml/gm (105, 106). These values will then be used to estimate regional blood flow.

For data analyses, all MRI markers will be measured for each kidney (left and right) for each subject and these two measurements for each specific MRI marker would be averaged to generate a summary measurement per subject for further statistical analysis. BOLD MRI measurements will be performed before and after administration of furosemide and the relative value (pre minus post) will be reported. The final averaged value will be analyzed statistically.

Summary of MRI Parameters:

| Renal Volume: | Left kidney volume (LKV), Right kidney volume (RKV) |
|--------------------|--|
| Diffusion Imaging: | ADC _{Left} (cortex), ADC _{Left} (medulla), ADC _{Right} (cortex), ADC _{Right} (medulla) |
| BOLD MRI: | R ₂ *(cortex) ^{pre} Left, R ₂ *(medulla) ^{pre} Left, R ₂ *(cortex) ^{pre} Right, R ₂ *(medulla) ^{pre} Right |
| | $R_2^*(cortex)^{pos}_{Left}$, $R_2^*(medulla)^{pos}_{Left}$, $R_2^*(cortex)^{pos}_{Right}$, $R_2^*(medulla)^{pos}_{Right}$ |
| | Pre – pre-furosemide; pos – post-furosemide |
| ASL MRI: | flow _{Left} (cortex); flow _{Right} (cortex) |

Data Management:

Data Entry

Data will be entered from paper forms. Once forms are completed, verified and corrected for inconsistencies, they will be manually entered using a HIPAA compliant, Red Cap database system.

Edit Checks

Computerized data validation routines will be used to enhance data quality and verify the accuracy of data within predefined value ranges. These checks include but are not limited to: (a) initial screening of data, using logic and range checks built into data entry screens; (b) cross-form functional and consistency checks; and (c) edits assessing the serial integrity of data.

Disaster Recovery

Routine data backup will occur on data in conjunction with the children's hospital secure server and Redcaps.

Security and Confidentiality

All hard copy forms will be de-identified with a study number and filed in a locked cabinet, to which only the investigators will have access. Standard protection against computer hackers is implemented. Recovery from natural disasters (water, fire, or electrical) can occur through the ability to reconstruct both the database management system and the data from nightly backups.

H. Summarize Knowledge to be Gained:

The innovative and novel pilot and feasibility trial aims to define the effects of coffee therapy on renal energetics and intrarenal hemodynamic function in youth with T1D. Carefully designed human studies, like the one proposed in this application, are needed to advance our understanding of the pathophysiology driving early DKD and direct the development of new therapeutic strategies to impede the development of DKD. Finally, the findings of this project could also inform other acute and chronic kidney disease conditions. The data obtained from this project will help delineate which renal processes are influenced by coffee consumption. The results and techniques from this project will be used to direct future collaborative clinical trials between Drs. [name] and [name].

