(2) Post-coffee visit (COFFEE Study #18-1874): Ten participants recruited from the CASPER Study, will be enrolled in the COFFEE Study. These participants will be provided with Starbucks® Cold brew 325ml bottles and instructed to drink one (1) bottle every morning between 6 and 9 am for 6 days. They will be asked to abstain from other caffeinated beverages and also decaffeinated coffee-based beverages for the duration of the study. During this time, they will also be instructed to follow the diet instructions (45% carbohydrates, 30% fat, 25% protein, a goal of 3.45 g salt/day). Six (6) days later, the participants will be return to CTRC for their follow-up (post-intervention) visit. The procedures of the post-intervention visit will match the pre-intervention visit. After obtaining fasting urine and blood, the participant will be asked to drink 1 bottle of Starbucks® Cold brew, after which they will undergo renal BOLD/ASL MRI at Brain Imaging Center, followed by quantification of GFR and ERPF by iohexol and PAH clearance studies during clamped mild hyperglycemia. Upon completion of GFR and ERPF measurements, participants will be provided with lunch, which concludes the study (we will not repeat DXA since it is unlikely that it will significantly change in 7-30 days, and it is not a study objective for this pilot and feasibility trial). Preferably participants will complete the post-intervention study 7 days after the pre-intervention study, but to facilitate recruitment we will allow participants to start the 7 days of coffee therapy followed by the post-intervention study within 30 days of the pre-intervention study.

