Visit 1 (Screening visit): Prescreening will be done by phone or in conjunction with a clinical diabetes visit. The full screening visit will include the consent process, history, allergies confirmed, physical exam, and screening labs (HbA1c, hemoglobin and hematocrit [H&H], serum creatinine, urine microalbumin to creatinine ratio). All females will also have a pregnancy test and detailed menstrual history. The screening visit will take approximately 2 hours.

Visit 2, part 1: Participants will present the evening before the study visit, or present fasting to the Pediatric CTRC in the morning, and have IV(s) placed. Fasting blood will be drawn for serum copeptin, lipids, insulin, cystatin c, creatinine, sodium, hematocrit and total protein prior to the clamp. Participants will be escorted to the Brain Imaging Center or CHC Radiology for a BOLD and ASL MRI per local protocol. BOLD MRI measurements will be performed at baseline and following administration of a small dose of furosemide (20 mg IV) via the PIV. A study physician or nurse will be responsible for the furosemide administration. Total duration of part 1 will be approximately 1.5 hours.

Visit 2, part 2: Participants return to pediatric CTRC and will have their blood glucose concentrations clamped in the hyperglycemic range. Participants will also undergo iohexol and PAH clearance studies, in addition to 4-hour urine collection for album excretion rate (AER) and albumin to creatinine ratio (ACR). Upon completion of visit 2, participants will be provided with a study meal (lunch). After lunch, participants will undergo DXA scan for quantification of body composition. This concludes the study. Total duration 6 hours.

Post-coffee visit (COFFEE Study):

Visit 3, Part 1: Participants will present the evening before the study visit, or present fasting to the Pediatric CTRC in the morning, and have IV(s) placed. Fasting blood will be drawn for serum copeptin, lipids, insulin, cystatin c, creatinine, sodium, hematocrit and total protein prior to the clamp. Participants will be asked to drink 1 bottle of Starbucks® Cold brew before being escorted to the Brain Imaging Center or CHC Radiology for a BOLD and ASL MRI per local protocol. BOLD MRI measurements will be performed at baseline and following administration of a small dose of furosemide (20 mg IV) via the PIV. A study physician or nurse will be responsible for the furosemide administration. Total duration of part 1 will be approximately 1.5 hours.

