Visit 3, part 2: Participants return to pediatric CTRC and will have their blood glucose concentrations clamped in the hyperglycemic range. Participants will also undergo iohexol and PAH clearance studies, in addition to 4-hour urine collection for album excretion rate (AER) and albumin to creatinine ratio (ACR). Upon completion of visit 2, participants will be provided with a study meal (lunch). This concludes the study. Total duration 6 hours.

A. Outcome Measure(s):

Aim 1:

- Renal oxygenation (R2*) by BOLD-MRI
 - Before and after Lasix
- Renal perfusion by pCASL MRI

Aim 2:

- GFR by iohexol clearance
- ERPF by PAH clearance
- Tubular injury markers (e.g. NGAL, KIM-1, IL-18, MCP-1, YKL-40)

| Table 2: Eligibility Criteria | | |
|------------------------------------|--|--|
| Inclusion criteria | Exclusion criteria | |
| Antibody+ T1D with <10 yr duration | Severe illness, recent DKA | |
| Age 12-21 years BMI ≥ 5%ile | eGFR <60ml/min/1.73m ² or creatinine > 1.5mg/dl or history of ACR≥300mg/g | |
| Weight<350 lbs and > 57 lbs. | ACE inhibitors, angiotensin receptor blockers (ARB), diuretics, sodium-glucose co-transport (SGLT) 2 or 1 blockers, daily NSAIDs or aspirin, sulfonamides, procaine, thiazolesulfone or probenecid, atypical antipsychotics and steroids | |
| Previous exposure to caffeine | Tachyarrhythmias, ADHD, tremors, tics, Tourette's, arrythmias, insomnia and overactive bladder Anemia or allergy to shellfish or iodine | |
| HbA1c <12% | Pregnancy or nursing MRI scanning contraindications (claustrophobia, implantable devices, >350 lbs) | |

B. Description of Population to be Enrolled:

Study Design and Research Methods

Study Diet: Participants will be instructed to follow a study diet 3 days prior to visit 2 (CASPER #17-0820), and between visit 2 and visit 3 (COFFEE #18-1874). The diet will be composed of 45% carbohydrates, 30% fat, 25% protein, goal of 3.45g of salt/day and will have no caffeine (besides what is provided in the cold brew), no decaffeinated coffee, regular soda or syrup, no candy as in our previous studies (58, 59)), as diet affects renal function.

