Iohexol clearance (GFR) and PAH clearance (ERPF): A bolus of iohexol (5mL of 300 mg/ml iohexol [Omnipaque 300, GE Healthcare]) will be given slowly over 2 min followed by a 10 ml normal saline flush, which will be time 0 for the iohexol clearance. 120 min will be allowed for equilibration of iohexol per or local protocol (62, 63). Blood for iohexol clearance will be drawn at +120, +150, +180, +210 and +240 min (62, 63). PAH (weight/75 x 4.2 ml) [University of Minnesota] will be given slowly over 5 minutes followed by a 10 ml normal saline flush. An infusion mixture of 8 mL of PAH and 42 mL of normal saline will be prepared in a 60mL syringe and infused in Syringe Pump at a rate of 24mL/hr, which will be time 0 of the PAH clearance. Ninety min will be allowed for equilibration of PAH per co-investigator [name] protocol (62, 63). Blood for PAH clearance will be drawn at +90 and +120 min (33-36). We will use Gomez' equations to calculate parameters of intrarenal hemodynamics (56, 64) (Table 2, pg. 5). Hyperfiltration by measured GFR (iohexol) will be defined

as ≥135ml/min/1.73m² (23, 65-67). The iohexol and PAH infusion period lasts 240 minutes and will occur concurrently with the mildly hyperglycemic clamp during which time the subject will rest in bed in the pediatric CTRC. During the entire 240-minute glucose/insulin infusion period, a pediatric CTRC nurse will remain at the bedside, and a Study Physician or Pediatric Nurse Practitioner or Pediatric Physician Assistant will also remain at the bedside to minimize any risks associated with iohexol and PAH infusion. The IV site will be continuously monitored to minimize risk of IV infiltration. De-identified coded blood samples will be sent to collaborator [name] lab at NIH/NIDDK who will run iohexol and PAH clearance on a HPLC platform (as per #16-1752, #17-0820, #18-0704).

RVR and Gomez equations (**Table 4**): RVR will be calculated as RVR = MAP/RBF. To derive additional information about intrarenal hemodynamic function we will use mathematical equations by Gomez et al (55). By using measurements of GFR, RBF, ERPF, renal vascular resistance, hematocrit and serum protein, we can calculate afferent and efferent arteriolar resistance (R_A and R_E), glomerular pressure (P_{GLO}) and filtration pressure (**Table 4**).

| Table 4 Measures | Definition: |
|------------------------------|---|
| Filtration fraction | FF = GFR / RPF |
| (FF) | (renal plasma flow) |

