| Renal blood flow | RBF = RPF (1-Hct) |
| (RBF) | |
| Renal vascular | RVR = MAP/RBF |
| resistance (RVR) | |
| Filtration pressure | $\Delta P_F = GFR/K_{FG}, K_{FG}$ |
| ΔP _F | filtration coefficient |
| Mean plasma | C_M = total protein / |
| protein (C _M) | FF x natural log |
| | (1/1-FF) |
| Glomerular oncotic | π _G = 5 x (C _M – 2) |
| pressure (π _G) | |
| Glomerular pressure | $P_{GLO} = \Delta P_F + P_{BOW} +$ |
| (P _{GLO}) | π_G , PBOW is 10 mmHg |
| Afferent arteriolar | R _A = [(MAP- |
| resistance (R _A) | P _{GLO})/RBF] x 1328 |
| Efferent arteriolar | R _E = [(GFR/K _{FG} x |
| resistance (R _E) | (RBF-GFR))] x 1328 |

Blood pressure: After participants have been laying supine for a minimum of 5 minutes, blood pressure measurements will be obtained using an automatic blood pressure machine and 3 measurements will be averaged. MAP will be calculated from the blood pressure readings.

Albumin excretion: ACR and AER be determined from 4 hr. urine collection.

Plasma tubular injury markers: NGAL and KIM-1 will be measured from fasting plasma samples on a Meso Scale Discovery Electrochemiluminescence (MSD-ECL) platform at [name] lab at John Hopkins, Baltimore, Maryland.

Fractional excretion of sodium (FeNa): We will measure serum and urine sodium and creatinine to calculate fractional excretion of sodium.

DXA: Participants will also undergo DXA by standard methods on a Hologic device (Waltham, MA) to determine lean and fat mass (72).

C. Description, Risks and Justification of Procedures and Data Collection Tools:

- 1. Study Duration: The anticipated duration for this add-on study is 2 years
- 2. Duration of Participation for Each Subject: 7 days
- **3. Sources of Research Material:** The patient's medical record will be reviewed for diabetes diagnosis, medications, allergies and other diagnoses that may disqualify patient from participation.

| Table 6: Data to be collected during study | |
|--|------------------------|
| Blood and Urine Samples | Blood pressures and HR |
| Questionnaires | Hyperglycemic clamp |
| DXA | lohexol clearance |
| Anthropometric measurements | PAH clearance |
| ASL and BOLD MRI | |

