Blood Samples: The collection of blood samples may result in temporary discomfort, bruising, bleeding, and on rare occasions, infection. EMLA cream helps to prevent discomfort, and sterile technique helps to minimize these risks. Nationally, the NIH Clinical Center has a guideline of 9mL/kg in 6-8 weeks for pediatric studies. Certain studies at our institution do draws over 7mL/kg in 6 weeks, or up to 7 mL/kg in a single draw but include iron supplementation. The screening visit (visit 1) will include 5 ml or less of blood (1 tsp) (HbA1c, H/E). The clamp and renal infusion studies (visit 2) includes 66mL of blood, which includes 48 mL from the clamp and 18 mL from the iohexol and PAH clearance studies. Thus, the clamp and renal infusion studies for subjects 26 kg or greater. This is highly unlikely to exclude many subjects, as we are recruiting adolescents between ages 12 and 18 and excluding, and subjects with BMI<5% (due to potential undiagnosed illness), those groups likely to be the lightest in weight. Therefore, we will limit recruitment to subjects 26 kg or greater. In addition, by study design, subjects <5% for weight are excluded as are subjects with anemia, screened by our baseline H/H, further increasing the safety of the study regarding blood draws.

IV risks: There is temporary discomfort when the needle goes in and 10% of the time there is a small amount of bleeding under the skin that may produce a bruise. Rarely, there is a risk of a blood clot formation, infection or infiltration. EMLA cream helps to prevent discomfort and sterile technique by experienced pediatric nurses help to minimize these risks.

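### Three formulas in Table 4 (RBF, R_E and C_M) are wrong as they read in the text; the derived hemodynamic parameters are at risk, the listed outcomes are not

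*Combined protocol and SAP*

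**What the plan says.** In the combined protocol and SAP, section IV (Research Methods), the paragraph introducing Table 4 commits to two calculations: "RVR will be calculated as RVR = MAP/RBF", and "To derive additional information about intrarenal hemodynamic function we will use mathematical equations" to obtain R_A, R_E, glomerular pressure and filtration pressure. Table 4 is the only place where the formulas are given. Three rows matter here:

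- **RBF:** "Renal blood flow | RBF = RPF (1-Hct", followed by a closing bracket. Nothing stands between RPF and the bracket. The FF row defines RPF as renal plasma flow.
- **R_E:** GFR/K_FG × (RBF-GFR), all inside one bracket, times 1328.
- **C_M (mean plasma protein):** total protein / FF × the natural log of (1/1-FF).

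The rows they connect with are FF = GFR/RPF; ΔP_F = GFR/K_FG; π_G = 5 × (C_M - 2); P_GLO = ΔP_F + P_BOW + π_G, where "PBOW is 10 mmHg"; RVR = MAP/RBF; and R_A = [(MAP - P_GLO)/RBF] × 1328.

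Hematocrit is measured at both visits. The descriptions of Visit 2, part 1 and Visit 3, part 1 each state "Fasting blood will be drawn for serum copeptin, lipids, insulin, cystatin c, creatinine, sodium, hematocrit and total protein prior to the clamp".

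The Outcome Measures section lists R2*, renal perfusion, GFR, ERPF and tubular injury markers. It does not list RBF, RVR, R_A, R_E or P_GLO.

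**The concern.** The RBF row makes whole-blood flow smaller than the plasma flow that is part of it, at any non-zero hematocrit. The R_E row multiplies the table's own filtration pressure by a flow, whereas R_A, with the same constant, divides a pressure by a flow; both cannot be resistances. The C_M row, read literally, takes the log of a number below one and returns a negative protein concentration.

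Specific aim 2 concerns intrarenal hemodynamic function, and the protocol says that the pilot will inform a larger trial. If the rows are followed as printed, absolute values on the wrong scale could be reported and carried forward. In addition, any change in hematocrit between the visits would push RVR in the wrong direction.

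**Working it through.** The plan gives no worked values for these quantities, so there is no figure to reproduce. The documents supply the formulas and P_BOW. **Everything else is assumed:** Hct 0.35 to 0.45; FF 0.15 to 0.25 for the R_E range; and, for the worked example, GFR 150 and RPF 750 mL/min (FF 0.20), Hct 0.40, MAP 85 mmHg, total protein 7 g/dL, K_FG 0.1 mL/s/mmHg. In the R_A and R_E rows, flows are converted to mL/s.

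**1. RBF.** By the definition of hematocrit, RPF = RBF × (1-Hct), so RBF = RPF/(1-Hct). Printed over correct is therefore (1-Hct)². RVR and R_A have RBF as denominator, and P_GLO does not contain RBF, so both are inflated by the inverse.

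| Assumed Hct | Printed/correct RBF | RVR and R_A too high by |
|---|---|---|
| 0.35 | 0.65² = 0.4225 | 2.37 |
| 0.40 | 0.60² = 0.360 | 2.78 |
| 0.45 | 0.55² = 0.3025 | 3.31 |

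Example: RBF is 750 × 0.60 = 450 mL/min printed and 750/0.60 = 1250 correct. RVR is 85/450 = 0.189 against 85/1250 = 0.068 mmHg/(mL/min).

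**2. R_E.** GFR/K_FG is ΔP_F, a pressure: (150/60)/0.1 = 25 mmHg. To be a resistance, as R_A is, the row must be [GFR/(K_FG × (RBF-GFR))] × 1328. With that bracket repaired but RBF as printed, printed over correct is [1/(1-Hct) - FF]/[(1-Hct) - FF]:

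- Hct 0.35, FF 0.15: 1.388/0.500 = 2.78
- Hct 0.40, FF 0.20: 1.467/0.400 = 3.67
- Hct 0.45, FF 0.25: 1.568/0.300 = 5.23

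Example: 25/5 × 1328 = 6640 with printed RBF (450 - 150 = 300 mL/min = 5 mL/s), against 25/18.33 × 1328 = 1811 with correct RBF (1250 - 150 = 1100 mL/min = 18.33 mL/s).

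**3. C_M.** Read literally, (1/1-FF) = 1 - FF = 0.80.

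| | Literal | With 1/(1-FF) |
|---|---|---|
| C_M = (7/0.20) × ln(·) | 35 × (-0.2231) = -7.81 | 35 × 0.2231 = 7.81 |
| π_G = 5 × (C_M - 2) | -49.05 | 29.05 |
| P_GLO = 25 + 10 + π_G | -14.05 mmHg | 64.05 mmHg |

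R_A then also changes, because it uses P_GLO. With RBF corrected (20.83 mL/s), (85 + 14.05)/20.83 × 1328 = 6314, against (85 - 64.05)/20.83 × 1328 = 1335.

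**4. Change between visits.** At constant Hct within a participant, (1-Hct)² cancels, so the percent change in RVR and R_A is unaffected by the RBF row. For R_E the factor also contains FF, so it cancels only if FF is unchanged too. If Hct moves from H0 to H1 at constant RPF and MAP, the RVR change is (1-H0)/(1-H1) - 1 as printed and (1-H1)/(1-H0) - 1 when correct:

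- 0.40 to 0.41: 0.60/0.59 - 1 = +1.7% printed; 0.59/0.60 - 1 = -1.7% correct
- 0.40 to 0.42: 0.60/0.58 - 1 = +3.4% printed; 0.58/0.60 - 1 = -3.3% correct

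The two versions point in opposite directions only while RPF itself changes by less than about 1.7% or 3.4% respectively.

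**5. What does not move.** FF and ΔP_F use none of the three rows. C_M, π_G and P_GLO do not use RBF. R2*, perfusion, GFR, ERPF and the tubular markers use nothing from Table 4.

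**The case against.** The RBF row is a machine-read cell from a narrow, broken table, and one dropped slash would explain it. That stands, and it makes this part conditional on the original. Slashes did survive in the FF, RVR, ΔP_F, C_M, R_A and R_E rows, so a genuine omission is plausible but not proven.

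The R_E and C_M rows might be called informal notation that a specialist would read correctly. Their brackets balance, however, so nothing has visibly been lost. The two rows also need opposite conventions: in C_M the slash must apply to FF alone, while in R_E it must apply to the whole product that follows.

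The text also points to a published set of equations, and the analysis code may follow those instead of Table 4. The documents do not settle this, so it stands as a limit.

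A reader might infer that aim 2 itself is compromised. It is not: its hypotheses name GFR, ERPF and tubular markers only. The analysis plan names no test of the derived parameters, and its power statement covers renal oxygenation and tubular injury markers.

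A reader might also infer that tests on RVR would often give a different verdict. No such rate can be stated, because the documents give no hematocrit, plasma flow or variability values.

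Finally, the blood-draw figure might be taken to bound the hematocrit shift: "The clamp and renal infusion studies (visit 2) includes 66mL of blood". It does not. That figure is itemised as 48 mL for the clamp plus 18 mL for the clearance studies, and the fasting samples are not itemised within it. A shift is plausible given the interval ("Preferably participants will complete the post-intervention study 7 days after the pre-intervention study"), but its size and direction are unknown: blood loss would lower hematocrit, and the hypothesised natriuresis could raise it.

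**Conclusion.** Three rows of Table 4 are wrong as they read; for RBF this is subject to the original. If they are followed:

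- The RBF row puts RBF at 0.42 to 0.30 of its true value, and RVR and R_A 2.4 to 3.3 times too high, over assumed Hct 0.35 to 0.45.
- R_E is not a resistance as bracketed. With the bracket repaired but RBF as printed, it is 2.8 to 5.2 times too high over that Hct range and assumed FF 0.15 to 0.25.
- The C_M row corrupts C_M, oncotic pressure, P_GLO and R_A, with a P_GLO of about -14 mmHg in the assumed example. The damage is therefore not confined to quantities built on RBF.
- A within-participant hematocrit shift enters RVR with the wrong sign, by roughly 1.7% per 0.01 of Hct near 0.40.

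The listed outcomes, the hypotheses and the power statement are untouched. Severity is minor: these are formula errors in additional, derived parameters of a hypothesis-generating pilot, and the documents do not show that the printed rows will be used in the calculation.

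**What to change.** Check Table 4 in the original file. Then print:

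- RBF = RPF/(1-Hct), if the slash is absent there too
- R_E = [GFR/(K_FG × (RBF-GFR))] × 1328
- C_M = (total protein/FF) × ln[1/(1-FF)]

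Confirm that the analysis code uses these forms, and that it uses the same forms for the pre-coffee visit, which is carried out under the parent CASPER protocol, and for the post-coffee visit. The cost is three table rows and one code check, with no new data and no change to the design.
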